- If a patient treated does not get pregnant within the 12 months of pre-conception phase, she terminates the study. She may keep the loaned devices for another 3 months unless it is needed for another patient. Data are not reported in eCRF, neither uploaded into CareLink Clinical for this period of time.
- If she stops using CSII for longer than 14 consecutive days during the study period
- If she stops coming to the follow-up visits (lost to follow-up)

If a patient is withdrawn from the study, the reason for withdrawal shall be recorded in the eCRF and in the patient's hospital record. If discontinuation is because of safety or lack of effectiveness, the patient shall be asked to be followed for collecting safety data.

Withdrawn subjects will be replaced until the number of 100 patients with full follow-up (pre-conception, conception, pregnancy, delivery, 6 weeks of lactation) is reached.

F.8 Study deviations and CIP changes

A study deviation is an event where the investigator or site personnel did not conduct the study according to the Clinical Investigational Plan, protocol, or Clinical Investigation Agreement. The investigator is not allowed to deviate from the above mentioned documents except with prior approval and under emergency circumstances. All deviations shall be documented and explained, regardless the reason for the deviation.

Medtronic retains the right to require the withdrawal of investigator / Investigational Site that violates the protocol.

The following deviations may impact subject safety, affect the integrity of study data and/or affect subject's willingness to participate in the study.

Examples (the list of examples is intended as a guide and is not all-inclusive):

- Failure to obtain informed consent, i.e., there is no documentation of informed consent
- Enrollment of a subject who did not meet all inclusion/exclusion criteria
- Failure to report serious adverse event to sponsor
- Device dispensing error (i.e., use of an investigational device on a non-study subject)

If monitoring and/or auditing identify serious and/or persistent non-compliance on the part of an Investigator/Investigational Center, the Sponsor should terminate the Investigator/institution's participation in the trial.

The Investigator shall notify Medtronic within 5 days of the following deviations:

- A deviation to protect the life or physical well-being of a subject in an emergency
- Failure to obtain informed consent or use the appropriate informed consent form
- Enrollment of a subject not meeting the eligibility criteria
- Inappropriate use of the study device (i.e., use of an investigational device on a non-study subject)

No preapproval of any deviations will be granted. If deviations occur they must be reported.

Medtronic will assess the significance of all deviations and evaluate the need to amend the Clinical Investigation Plan or to early terminate the investigation, in accordance with Medtronic internal SOPs.

F.8.1 Request for approval of study deviations

The investigator shall obtain documented approval from Medtronic, before implementation, for any change in or deviation from the Clinical Investigation Plan. The investigator shall timely contact the Clinical Research Specialist or designee for review of the proposed change/deviation.

Prior approval is not always realistic in situations where unforeseen circumstances are beyond the investigator's control. However, also in these cases the event is considered a deviation, and shall be reported.

In any emergency situation the investigator shall exercise his/her judgment to safeguard the subject's interest. Such deviations from the Clinical Investigation Plan do not require the prior approval of Medtronic. The investigator shall report the deviation as soon as possible to Medtronic.

F.8.2 Reporting requirements for study deviations

The investigator shall adhere to EC/IRB requirements and procedures for reporting study deviations.

Medtronic is responsible for analyzing deviations, assessing their significance, and identifying any additional corrective and/or preventive actions (e.g. amend the CIP, additional training, terminate the study, etc.). Repetitive or serious investigator compliance issues may result in the need to initiate a corrective action plan, and in some cases freeze enrollment or ultimately terminate the investigator's participation in the clinical study. Medtronic will provide investigation site-specific reports to the investigators on a periodic basis summarizing information on deviations that occurred at the investigational site.

F.8.3 Amendments to the Clinical Investigation Plan

The investigator will propose any appropriate modification(s) of the Clinical Investigation Plan or investigational device or investigational device use. Medtronic will review this proposal and decide whether the modification(s) will be implemented.

G QUALITY CONTROL PROCEDURES

G.1 Procedures for database management

G.1.1 Data collection

An Investigator Site File (ISF) will be handed-out upon initiation.

The investigator must ensure accuracy, completeness and timeliness of the data reported in the CRFs and in all other required reports. Data reported on the CRFs which are derived from source documents must be consistent with the source documents or the discrepancies need to be justified in a documented rationale, signed and dated by the (principal) investigator, to be filed in the patient file.

Only authorized persons can complete CRFs as specified on the DTL. CRFs shall be signed and dated by investigators (physician) as specified on the Delegated Tasks List included in the Investigator Site File.

The Electronic Data Capture (EDC) system maintains an audit trail on entries, changes or corrections in CRFs. If a person only authorized to complete CRFs makes changes to an already signed CRF, the investigator shall re-sign this CRF.

The pump data will be uploaded into CareLink Clinical.

A printed copy of the eCRF Forms to be used in this study will be kept separately of the CIP. In case EDC system would fail, paper copies of the eCRF forms can be made in order to be able to continue collection of study data.

All data is recorded in the medical records, and entered to the eCRF at data collection points.

G.1.2 Time windows for completion and submission of Case Report Forms

The investigator must ensure accuracy, completeness, legibility and timeliness of the data reported in the eCRFs and in all other required reports. Data reported on the eCRFs which are derived from source documents must be consistent with the source documents or the discrepancies need to be justified in a documented rationale, signed and dated by the investigator.

The eCRF shall be completed no later than three (3) weeks after patient visit and signed and submitted not later than four (4) weeks after patient visit.

SAE and SADE data must be reported immediately.

G.1.3 Data review and processing

Data management will be done according to Medtronic internal SOPs. These documents will be made available on request.

A minimum of 25% of total patient data Case Report Forms (CRFs), calculated from the total number of separate case report forms determined to be source verifiable and received in the database, will be source verified before database freeze for the final report without possibility on verification by person from Medtronic.

Priority of source data review should be given to the following electronic Case Report Forms: Baseline Data (demographic data, glycemic control, HbA1c), first follow-up during pregnancy week 12 – glycemic control, HbA1c), last follow-up during pregnancy (week 36 – glycemic control, HbA1c), 6-week follow-up during lactation phase (neonatal data, neonatal care admissions). The 6-week visit in lactation phase would include any preterm delivery CRFs that have been completed. In addition, all procedure related Adverse Events will be monitored 50% and applicable copies of source data will be sent to the Clinical Safety Specialist. No patient identifiable data may appear on these copies.

Monitoring activities may include, but are not limited to, review of regulatory documents patient informed consent documentation. In addition, any applicable local laws and regulations will be followed. Control visits will be documented via a Monitoring Visit Report. The monitoring report is reviewed by the Study Manager to ensure that the sites follow the protocol, and that all the regulatory requirements are fulfilled. The findings in the report will be translated into actions to resolve any issues observed. The Monitoring Visit Follow-up Letter will be sent to the Principal Investigator.

G.2 Monitoring procedures

Monitoring visits will be conducted at the start, during and at the closure of the clinical study in accordance with Medtronic internal SOPs and the Monitoring Plan.

Site initiation of the study will be conducted by HTA Consulting. Medtronic monitors may take part in site initiation too. Site closure will be conducted by HTA Consulting and Medtronic monitors. Regular monitoring visits during the study will be conducted by the Medtronic monitors according to the Monitoring Plan that will be kept separately from this CIP.

G.2.1 Accessibility of investigation site staff and study materials

The principal investigator(s), his/her delegate(s) and the study coordinator(s) shall be accessible to Medtronic personnel involved in the study management and monitoring. This accessibility is of particular importance for reviewing data in the Case Report Form (CRF). Direct access to patient records for source data verification will need to be granted and prepared prior to any monitoring visits.

G.2.2 Audits and investigation site inspections

In addition to regular monitoring visits, Medtronic may conduct audits at participating investigation sites. The purpose of an audit is to verify the adequate performance of the study related activities. Independent of the employees involved in the study. Regulatory bodies may also perform inspections at participating investigation sites.

The investigator and/or institution shall permit Medtronic and regulatory bodies direct access to source data and documents, taking into account any restrictions due to local law, to perform study-related monitoring, audits, and regulatory inspections.

Any competent authority announcements shall be forwarded to the Study Manager. Investigation sites will be required to provide access to source documents and data to the bodies mentioned above.

G.3 Study suspension or early termination

G.3.1 Early study suspension or termination

Medtronic may decide to suspend or prematurely terminate the study (e.g. if information becomes available that the risk to study subject is higher than initially indicated, if interim analysis indicates that the results significantly differ from the study objectives or statistical endpoints, or because of a business decision). If the study is terminated prematurely or suspended, Medtronic shall promptly inform the clinical investigators of the termination or suspension and the reason(s) for this. Principal Investigators will also promptly inform the study participants about the termination or suspension of the study.

G.3.2 Early investigation site suspension or termination

Medtronic may decide to suspend or prematurely terminate an investigation site (e.g. in case of non-compliance to the Clinical Investigation Plan or lack of data collection requirements). If an investigation site is suspended or prematurely terminated, Medtronic shall promptly inform the clinical investigator(s) of the termination or suspension and the reason(s) for this. If proper correction is made, and suspension of the investigation site is lifted, Medtronic shall promptly inform the principal investigator(s) about the change and the reason(s) for the change. The principal investigator(s) will inform the study participants.

G.3.3 Subject follow-up in case of termination

In case of early termination of the study all patients already enrolled will be called into hospital for a closing visit. During this visit, it will be up to the investigator to decide whether the patient can keep using the loaned devices or not.

G.4 Study close out

After all patient follow-ups have been completed; the Medtronic monitors will visit each center. During this visit, the monitors will discuss and verify the following items for study closure:

- Remaining action items closure
- Final study payments
- Investigator Agreement termination
- Archiving and storage of study documents, in adequate space.

At the study site, study documents and all source documents must be retained at least 20 years after study closure.

When all CIP requirements have been met or if for any reason the study is terminated, a letter describing the status of the final study responsibilities will be provided to principal investigator.

H DATA ANALYSIS AND REPORTING

A Biostatistical Plan (BP) will be prepared and kept separately from the CIP.

H.1 Analysis of clinical data

H.1.1 Analysis of Primary Objectives

Descriptive analysis will be performed for all available groups: 1) all enrolled; 2) those who failed to achieve a pregnancy; 3) those who become pregnant after the pre-conception phase; 4) those who already pregnant and enrolled after.

Glycemic control measured by HbA1c

Calculate descriptive statistics for HbA1c

- A1C and change of A1c
 - from baseline
 - each Pregnancy trimester
- Proportion of subjects achieving A1C < 6% (6.5%, 7%, 7.5%, 8%)

Glycemic Control measured by Continuous Glucose Monitoring Data (for subjects with available sensor data (SG) only)

Calculate descriptive statistics for Sensor glucose distribution, the following variables will be analyzed as overall and stratified by pregnancy outcome (no conception, delivery, miscarriage, etc.) and completeness of treatment phase (complete follow-up, pregnancy and 6 weeks after delivery, pre-conception phase only, etc.)

- Mean SG per subject per day
- SG variation (CV, SD, MAGE) per subject per day
- % of SG < 50mg/dL, 50-60mg/dL, 60-70mg/dL, 70-120mg/dL, 120-140mg/dL, 140-180mg/dL, 180-250mg/dL and > 250mg/dL per subject per day
- AUC of SG < 50mg/dL, < 60mg/dL, < 70mg/dL, > 140mg/dL, >180mg/dL and > 250mg/dL

per

- Pregnancy trimester
- Duration of treatment received
- Sensor compliance (% of time sensor wear) in SAP group only

The analysis will be repeated for listed variables based on 2-hour postprandial CGM data and night only (10pm to 7am) data.

Glycemic Control measured by SMBG Data

Calculate descriptive statistics for SMBG distribution, the following variables will be analyzed as overall and stratified by pregnancy outcome (no conception, delivery, miscarriage, etc.) and completeness of treatment phase (complete follow-up, pregnancy and 6 weeks after delivery, pre-conception phase only, etc.)

- N, Mean, Median, SD, Min and Max per subject per day per
- Pregnancy trimester
- Duration of treatment received

H.1.2 Analysis of Secondary Objectives

Pregnancy Outcomes

Calculate incidence rates for the following events as overall and by duration of treatment received.

- Mode of Delivery
 - Normal
 - Elective CS
 - Emergency CS
- Preterm Delivery (< 37 weeks)
- Miscarriage (< 22 weeks or \geq 22 weeks)
- Neonatal Morbidity
 - Neonatal Hypoglycaemia
 - Other
- Other Pregnancy Related Serious Adverse Events

Neonatal Outcomes

Calculate descriptive statistics for the following as overall and by duration of treatment received.

- Respiratory Distress
 - 1 and 5 minute Apgar scores
- Infant Birth Weight
 - SD scores
 - Customised birth weight percentile (LGA, SGA)

Provide frequency tables for the following variables

- Neonatal Morbidity
 - Treatment for Neonatal Hypoglycaemia

- Neonatal Care Admission
 - Duration of Stay
 - Level of Care

- Feeding at Hospital Discharge
 - Breast
 - Bottle
 - Both

Questionnaire and Surveys

The questionnaire and survey results will be presents and by time of questionnaire/survey collected

- Hypoglycaemia Fear Survey (HFS)
- Diabetes Treatment Satisfaction Questionnaire
 - DTSQs
 - DTSQc

Other Maternal Outcomes

Calculate descriptive statistics for the following variables

- Weight
- BMI
- Daily Insulin Requirements (units) at the moment of the visit
- Microalbumin excretion with albumin/creatinine ratio
- Number of SMBG per subject per day (patient self-reported)

per

- Pregnancy trimester
- Duration of treatment received

Device Information at Delivery

Calculate the proportion of pump and/or sensor wear (yes/no) at time of delivery Summary survey results for patient satisfaction with treatment during delivery

Safety Analysis

All site reported adverse events for enrolled subjects will be summarized, including:

- Incidence of severe (clinical) hypoglycemia
- Incidence of DKA
- Serious adverse events (SAE)
- Unanticipated device effects (UADE)

Detailed information of all adverse events will be provided in listings. The summary of adverse events will also be provided per trimester.

Baseline Information and Demographic Characteristics

Baseline information and demographic characteristics such as age, gender, weight, BMI, diabetes duration, insulin regimen, etc. will be summarized. Medical information such as previous severe hypoglycemia and DKA history up to 12 month prior to study start will also be summarized.

Subject Disposition and Center Specific Information

Number of subject screened enrolled, withdrawal, complete of each pregnancy phase and study will be reported. The number of subjects assigned to CSII/SAP group, with or without sensor will also be provided as overall and for each center.

H.2 Publication Policy

A Publication Committee will be established.

Publications and presentations referring to the 'Pregnancy Observational Study in Poland' will be coordinated by the Publication Committee and Medtronic to allow the use of all available data.

All parties – the Publication Committee, Medtronic and the Orchestra Foundation – intend to publish the results of the registry in both international and local (Polish) medical journals.

The following publication policy will have to be adhered to by all participating investigation sites.

Authorship on any publication(s) resulting from this study will be assigned according to substantial contributions to conception and design, acquisition of data, or analysis and interpretation of data, drafting the article or revising it critically for important intellectual content and final approval of the version to be published. This is in accordance with the Vancouver principles (The Uniform Requirements for Manuscripts Submitted to Biomedical Journals: Writing and Editing for Biomedical Publication, ICMJE, October 2008), as agreed upon by the editors of all major medical journals.

The number of authors will be dependent on the regulations of the concerning journal with a maximum of 10 authors. Names of all participating investigators will appear in the Acknowledgment of the paper.

A single investigation site may access and use the data provided by itself for scientific publications following prior approval by the Publication Committee and the Orchestra Foundation.

Pooling data from several investigation sites for publication purposes, national projects and international projects all require prior approval from the Publication Committee and the Orchestra Foundation.

Medtronic can use the data and/or any results derived from the data or publications based on that data for marketing purposes, further research and development of devices or educational use after the approval by the Orchestra Foundation.

The study sponsor will collect data in such way that no patient can be identified, and monitor study records.

Participating patients will not be identified by name in any published reports about the study.

I STUDY MANAGEMENT

I.1 Study staff

This study is sponsored by

Medtronic Poland Spółka z ograniczoną odpowiedzialnością

[name]

[name]

[contact]

[contact]

An independent company, HTA Consulting, will be performing some activities of the study as described in this CIP, under the supervision of Medtronic.

The list of study staff contact details is listed in Annex K2.1.

The sponsor will maintain the list and provide updates if needed.

I.2 Advisory committees

A Steering Committee of medical advisers and Medtronic representatives was established.

The roles and responsibilities of the Steering Committee are documented in the separate Steering Committee Charter

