The devices to be used in the study are the Paradigm REAL-Time (722) insulin pump, including the sensor augmented Paradigm® Veo (754) system (insulin pump + Enlite sensor + MiniLink transmitter); all devices are CE-marked and manufactured by Medtronic. All devices are commercially released and used within their intended use. They are available and labelled in the local language as are the Instructions for Use.

- Paradigm® REAL-Time 722 insulin infusion pump (MMT-722)
- Paradigm® VEO™ Insulin Pump (MMT-754)
- Enlite® Sensor (MMT-7008) Enlite® Serter (MMT-7510)
- MiniLink™ Transmitter (MMT-7703)
- MiniLink™ Charger (MMT-7705) CareLink® USB (MMT-7305)
- Medtronic CareLink® Clinical Therapy Management Software for Diabetes (MMT-7334)
- Bayer® Contour Link™ BG Meter
- Another model or brand of BG Meter that is compatible with the CareLink Clinical software, if Bayer® Contour Link™ BG Meter is not available

Except for Enlite sensors that are for single use, all the devices are loaned to the study participants for the study period, and will be returned to the investigation site, and will be used by other eligible subjects.

Design

The project is designed as a multi-center prospective observational Post-Market-Release study to be conducted in up to 30 centers in Poland.

Total duration of the study per patient will be up to 22 months (up to 12 months pre-conception phase, pregnancy, and 6 weeks after delivery). The optimal study start is the beginning of pre-conception phase, however, pregnant women up to the 16th week of pregnancy can participate in the study too. The study end is 6 weeks after delivery. If conception does not occur within 12-months, the patient's study participation is terminated, and the insulin pump might be taken away from the patient. The following therapy is decided by the investigator. If the pump is not taken away after the 12-month of trial period for conception, the patient can continue insulin pump therapy until the pump is needed for another patient.

The study started in May 2013; enrolment period is planned for 30 months which can be modified by the decision of the Steering Committee. The final report will be available within 24 months after the end of enrolment.. Data collection will be stopped when data have been collected from 100 pregnancies with complete follow-up (including pre-conception phase, pregnancy, delivery and 6 weeks of lactation).

Treatment

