The Enlite serter is used to ensure correct placement of the Enlite sensor. The Enlite serter inserts the sensor at a 90-degree angle and injects the sensor into the insertion site when the button is released. The Enlite serter also minimizes sharps exposure, facilitates adhesive cover removal, and supports one hand insertion without visual access. The Enlite serter is intended

for single patient, multi-use device. The Enlite senter is manufactured by Medtronic. Its intended use is to insert the Enlite sensor.

- **MiniLink™ Transmitter (MMT-7703)**

The Medtronic MiniLink™ transmitter (MiniLink) is a component of continuous glucose sensing systems and sensor augmented insulin pump systems. The MiniLink powers the glucose sensor, collects glucose data, and wirelessly sends the data to a monitor. The monitor is a Medtronic continuous glucose sensing monitor or Medtronic MiniMed® sensor augmented insulin pump. The MiniLink Transmitter is part of the MiniLink system, manufactured by Medtronic. The intended use is to transmit data to the Medtronic insulin pump.

- **MiniLink™ Charger (MMT-7705)**

The charger is used to recharge the MiniLink battery as needed. The charger is powered by a AAA battery intended to last for up to four months, and is designed for easy connection and disconnection from the MiniLink. The charger has a green light that shows the charging status and a red light that communicates any problems during charging. The full recharge lasts for up to 14 days of continuous use. After 14 days of use, the MiniLink can be fully recharged in less than 1 hour. The MiniLink charger is part of the MiniLink system, manufactured by Medtronic. The intended use is to charge the MiniLink.

- **CareLink® USB (MMT-7305)**

The Medtronic CareLink USB, is indicated for use commercially by patients at home and for clinicians in a medical office setting as a means of facilitating communication between Medtronic diabetes therapy management devices that use Paradigm-compatible RF telemetry and a personal computer that uses data management application software. The CareLink USB device will enable data from the pump to be uploaded to CareLink Clinical. The CareLink USB is part of the CareLink system, manufactured by Medtronic. The intended use is to connect the pump to a computer for data upload.

- **Medtronic CareLink® Clinical Therapy Management Software for Diabetes (MMT-7334),**

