This study will be conducted in compliance with the Declaration of Helsinki of 2008, laws and regulations of Poland in which the study is conducted, including data protection laws, the Clinical Investigation Plan, and clinical investigation agreement.

The principles of the Declaration of Helsinki have all been implemented in this study by means of the patient informed consent process, MEC approval, study training, clinical trial registration, risk benefit assessment, publication policy, etc.

E.4 Training requirements

Prior to investigation site activation or subsequent involvement in study activities, HTA Consulting (CRO) and Medtronic monitors will provide study training relevant and pertinent to the involvement of personnel conducting study activities and investigator responsibilities. The investigation site team will be trained on the study related procedures including the Clinical Investigation Plan, the Patient Informed Consent process, the data collection tools, and electronic data collection systems during the initiation visit, and training will be documented in the clinical project file (sponsor file) and investigator site file.

Performed training will be documented prior to investigation site activation.

E.5 Study materials and study-specific equipment

An Investigator Site File is provided to each initiated investigation site.

E.6 Study device/product traceability

Medtronic is responsible for the manufacturing, packaging, labelling and distribution of all study devices, all devices used in this study are CE marked and commercially available in Poland. They will be stored and used according to their IFU.

Devices have been purchased by the Orchestra Foundation and are delivered to the hospitals that are responsible for storage, handling and disbursement of the devices to each study participant.

Patients should receive supplies to the study devices (sensors for the SAP group) at each scheduled visit. The insulin pump and the MiniLink transmitter provided to each subject are identified by various numbering sequences (i.e. serial numbers, lot numbers, manufacturer numbers, etc.). The serial number (SN) should be recorded on a per subject basis in the Device Tracking Log.

Except for Enlite sensors which are given free of charge, all the devices are loaned to the study participants for the study period, and will be returned to investigation site, and will be used by another eligible subject.

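### The protocol describes the Enlite Serter as a single-patient device, but its loan-and-reuse rule exempts only sensors, so the sections contradict each other

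*Protocol*

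**What the plan says.** Four parts of the Protocol bear on this.

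- **B.2 Device information, Enlite Serter.** The Serter is intended "for single patient, multi-use device". A page break splits the sentence, but its subject is clearly the Serter.
- **A Synopsis, Medical devices.** The Serter (MMT-7510) is listed beside the sensor. The paragraph introducing the list says the devices are "used within their intended use". Below the list comes the loan rule: "Except for Enlite sensors that are for single use, all the devices are loaned to the study participants for the study period", after which they "will be returned to the investigation site, and will be used by other eligible subjects".
- **E.6 Study device/product traceability.** The rule is repeated: "Except for Enlite sensors which are given free of charge, all the devices are loaned to the study participants for the study period", and they "will be returned to investigation site, and will be used by another eligible subject". The same section says that devices are stored and used according to their instructions for use.
- **J.2 Risks.** Use in line with labelling is the stated reason for expecting no risks beyond those of routine device use.

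The SAP does not mention the Serter and does not repeat the loan rule.

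**The concern.** A site cannot apply the loan rule to the Serter and also respect the B.2 description. The rule has two parts, return and onward use, and its only exception is the sensor. The Serter is on the list that the rule refers to and has no exception of its own.

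The matter bears on patient safety, because the Serter places a sensor that penetrates the skin and the users are women who are pregnant or planning pregnancy. It also bears on J.2. If a device described as single-patient went to a second woman, the premise of labelled use behind the risk statement would no longer hold for that device.

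Site staff would act on this wording. Under E.2.2 the consent form tells the woman to whom and when to return devices, and Table 2 in F.3 schedules their return.

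**Working it through.** No arithmetic applies, and the plan has no figure on this point to reproduce. The check compares the texts.

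| Question | Where | Answer |
|---|---|---|
| Is the Serter a study device? | Synopsis device list; B.2 | Yes |
| How is its use described? | B.2 | Reusable, by one patient |
| Which devices are loaned, returned and passed on? | Synopsis; E.6 | All devices except Enlite sensors |
| Is the Serter exempted anywhere? | Protocol and SAP | No exemption found |
| What is promised about use? | Synopsis; E.6; J.2 | Within intended use; according to instructions for use; in line with labelling |

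1. *Does multi-use remove the conflict?* No. In B.2 the repeated use is qualified by the restriction to one patient. The loan rule concerns a second patient.
2. *Is the rule a single slip?* No. It appears in two sections, each time with sensors as the only exception. The stated reason differs: the Synopsis exempts sensors because they are single-use, E.6 because they are given free of charge. The Synopsis wording shows that a limit on re-use was considered when the exception was written, but the single-patient limit in B.2 was not carried across.
3. *Does the protocol say which statement prevails?* No. E.6 contains both the instructions-for-use statement and the pass-on rule, without ranking them.
4. *Can the number of women affected be derived?* No. The Synopsis plans sensor-augmented therapy for about one third of subjects, and C.6 expects 500, so 500 × 1/3 ≈ 167 women would be given sensors. That is not a count of women who would receive a previously used Serter. The first user of each Serter is not exposed, the number of Serters and of re-issues is not stated, and women who buy their own sensors are not included.

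**The case against.** The best counter-argument is that the rule's reference to all devices was never meant item by item. The Synopsis list includes CareLink Clinical, which is web-based software and cannot be loaned or returned. It also includes the CareLink USB, although B.2 says that only centre staff perform uploads in this study. F.2 even calls the sensor a loaned device, against the rule's own exception. E.6 requires serial numbers per subject only for the pump and the MiniLink transmitter, and the F.3 data tables record serial numbers only for those two. On this reading the rule concerns the main hardware, and the Serter is never individually named as loaned or re-issued. This stands as evidence of loose drafting. It does not remove the conflict, because the Serter is on the list directly above the rule and only sensors are excepted.

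A second argument is that a site reading the whole protocol would let the intended-use, instructions-for-use and labelling statements govern. That softens the point, but no order of precedence is given and the loan rule taken literally contradicts all three.

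Third, item-level return instructions may exist in the consent form or the device instructions, which are not available here. That is possible, so one cannot conclude that sites lacked correct guidance. The protocol text would still need to agree with such guidance.

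A reader might go further and infer that Serters were in fact shared between women, or that about 167 women were exposed. The documents support neither. They record no re-issue of a Serter, describe no harm from one, and the 167 counts women planned to be given sensors. B.2 says the Serter reduces sharps exposure, and it describes the introducer needle under the sensor, which the Synopsis makes single-use.

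**Conclusion.** The inconsistency is real and confined to one device. The description in B.2 conflicts with the loan rule in the Synopsis and E.6, and the rule, followed literally for the Serter, conflicts with three assurances about proper use. It is a drafting inconsistency with a possible safety consequence and does not reflect a design choice. The extent of any actual sharing is unknown.

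The conclusion assumes only that the loan rule is read as written and that the Serter belongs to the list it refers to. It makes no judgement on which handling of the Serter is right. Nothing in the sample size, the analysis sets or the descriptive analyses depends on it. It deserves correction because it touches patient safety and the remedy is small.

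**What to change.** The sponsor should reconcile the Synopsis (Medical devices), B.2 and E.6:

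- State, item by item, which listed devices the loan, return and re-use rule covers. One line in the Synopsis and a matching line in E.6 would do, with B.2 consistent with both.
- Send sites a short clarifying note that also covers any Serters already returned.
- Check that the return instructions in the consent form agree with the reconciled text.

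The cost is two lines of protocol text, one site note and one check of the consent form. No change is needed to data collection, sample size or the SAP.
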